16.1 Primary Endpoint

Safety:

- adverse events (AEs)
- tolerability including assessment based on PAERS
- Tanner score
- absolute values and changes from Baseline Extension A in clinical safety laboratory tests, vital signs, weight, height, and ECG parameters
- length of menstrual cycle
- potentially clinically significant clinical safety laboratory test values, vital signs, weight, and ECG parameter values relative to Baseline Extension A
- C-SSRS categorisation based on C-CASA definitions (1, 2, 3, 4, and 7)

16.2 Secondary Endpoints

Depressive symptoms:

- change from Baseline Extension A to Week 26 in CDRS-R total score
- time to first relapse (CDRS-R value of ≥ 40)
- time to first loss of remission (CDRS-R > 28)

Global Clinical Impression:

- change from Baseline Extension A to Week 26 in CGI-S score
- CGI-I score at Week 26. The assessment of the CGI-I should be in reference to Baseline A in the lead-in studies.

Cognitive function:

Children (7-11 years)

- change from Baseline Extension A to Week 26 in BRIEF using the Global Executive Composite score
- change from Baseline Extension A to Week 26 in BRIEF using the Metacognition Index

Adolescents (12-18 years)

- change from Baseline Extension A to Week 26 in BRIEF-SR using the Global Executive Composite score
- change from Baseline Extension A to Week 26 in BRIEF-SR using the Metacognition Index

Functionality:

- change from Baseline Extension A to Week 26 in CGAS score
- change from Baseline Extension A to Week 26 in PedsQL VAS

17 Statistical Methodology

17.1 Responsibilities

The Department of Biostatistics, H. Lundbeck A/S will perform the statistical analyses described below.

17.2 Analysis Sets

The following analysis sets will be used to analyse and present the data:

- all-patients-treated set (APTS) – all patients who took at least one dose of vortioxetine in the extension study.
- full-analysis set (FAS) –all patients in the APTS with at least one valid post-Baseline Extension A assessment of the CDRS-R total score.

The safety analyses will be based on the APTS.

The efficacy analyses will be based on the FAS.

17.3 Descriptive Statistics

In general, summary statistics (n, arithmetic mean, standard deviation, median, minimum and maximum values) will be presented for continuous variables and counts and, if relevant, percentages will be presented for categorical variables.

The data will be summarised for all patients, and by lead-in study and by lead-in treatment (lead-in Study 12709A and Study 12710A).

For some variables summaries will include data from the lead-in study.

17.4 Patient Disposition

Patient disposition will be summarised and include the number of patients who completed and the number of patients who withdrew from treatment, as well as the number of patients in each analysis set (APTS and FAS).

The number of patients who withdrew from treatment will be summarised by primary reason for withdrawal as well as by all reasons for withdrawal.

17.5 Demographics and Other Baseline Characteristics

Demographics (sex, age, race), other baseline (Baseline Extension A) characteristics (height, weight, BMI) for the extension study, and baseline efficacy variables for the extension study will be summarised.

17.6 Recent and Concomitant Medication

Recent and concomitant medication will be summarised by anatomical therapeutic chemical (ATC) code and generic drug name.

17.7 Exposure and Compliance

Exposure and compliance will be calculated per patient and summarised.

17.8 Efficacy Analyses

17.8.1 General Efficacy Analysis Methodology

Change from Baseline Extension A in CDRS-R, CGI-S, BRIEF, CGAS, and PedsQL VAS using descriptive statistics by lead-in study and by lead-in treatment.

CGI-I score at Week 26 using descriptive statistics by lead-in study and by lead-in treatment.

Time to first loss of remission and time to first relapse will be analysed using Kaplan-Meier estimates.

For exploratory use a random effects slope and intercept model will be applied using Mixed Model Repeated Measurements (MMRM) to study long-term development in efficacy parameters such as CDRS-R.

17.9 Pharmacokinetic Analyses

Sparse sampling (2 time points) for vortioxetine quantification will be performed. The population PK of vortioxetine will be assessed by means of nonlinear mixed effect modelling and the results from the analysis will be reported in a separate population PK report.

17.10 Safety Analyses

17.10.1 Analysis of Adverse Events

Adverse events will be classified according to the time of onset of the adverse event:

- *lead-in adverse event* – an adverse event ongoing from lead-in study 12709A or study 12710A and prior to the date of first dose of IMP in study 12712A
- *treatment-emergent adverse event* (TEAE) – an adverse event that starts or increases in intensity on or after the date of first dose of IMP in study 12712A.

Adverse events, sorted by system organ class (SOC) and preferred term, will be summarised.

TEAEs may be allocated into study periods (these will be defined in the *Statistical Analysis Plan*).

The primary objective will be addressed with an overall clinical evaluation of the safety results.

17.10.2 Analyses of Safety Endpoints

Adverse events, PAERS items, Tanner scores, clinical safety laboratory tests, vital signs, height, weight, BMI, and ECG parameters will be summarised, and observed potentially clinically significant (PCS) safety laboratory test values will be flagged and summarised. Length of menstrual cycle and C-SSRS scores will be summarised using descriptive statistics.

For variables that are heavily dependent on sex and age (such as Tanner and menstrual cycle length) further exploratory descriptions will be made.

Analyses will be performed with respect to the baseline in lead-in study 12709A or 12710A and Baseline Extension A.

For exploratory use a random effects slope and intercept model will be applied using Mixed Model Repeated Measurements (MMRM) to study long-term development in safety parameters such as weight.

17.11 Interim Analyses

No interim analyses for efficacy are planned. A DMC will monitor safety data at regular intervals to be specified in the Data Monitoring Committee Charter.

17.12 Sample Size and Power

No formal sample size calculation has been performed for the present study, which includes patients who have completed the studies 12709A or 12710A and are eligible for enrolment for this study. Sample size is based on an expected withdrawal of 15-20% of the 1200 patients randomised to the lead-in studies. A maximum of 85% of these lead-in completers are

expected to accept to continue into this extension study. This gives approximately 850 patients.

17.13 Statistical Analysis Plan

A *Statistical Analysis Plan* describing the handling of data issues and the planned statistical analyses in more detail will be prepared by the Department of Biostatistics, H. Lundbeck A/S.

18 Clinical Study Report and Publications

18.1 Clinical Study Report

Upon completion of the study, a *Clinical Study Report* will be prepared by the Department of Medical Writing, H. Lundbeck A/S.

18.2 Data Ownership

The data collected in this study are the property of H. Lundbeck A/S.

18.3 Publications

The results of this study will be submitted for publication.

The primary publication based on this study must be published before any secondary publications are submitted for publication.

Authors of the primary publication must fulfil the criteria defined by the International Committee of Medical Journal Editors (ICMJE).³⁸

19 Indemnity and Insurance

In the event of study-related injuries or deaths, insurance for the patients and indemnity of the investigators and those of their employees, servants, or agents whose participation in this study has been documented are provided. Insurance and liability will be in accordance with applicable laws and *Good Clinical Practice*.

20 Finance

20.1 Site Agreement

The financial agreements for the site are addressed in one or more documents. Both parties must sign the agreements before the site is initiated.

20.2 Financial Disclosure

All the investigators, including sub-investigators, and raters participating in the study must complete a *Financial Disclosure Form* in order to comply with the United States Food and Drug Administration (FDA) *Financial Disclosure* requirements.

Appendix II

Recent and Concomitant Medication: Disallowed or Allowed with Restrictions

Recent and Concomitant Medication: Disallowed or Allowed with Restrictions

In the table below disallowed recent and concomitant medications are listed, including any restrictions with respect to their use prior to and during the study.

Drug Class	Disallowed (X) During the Study for		
	Chronic Use	Episodic Use	Comments or Exceptions
Agents used for ADHD (non stimulant e.g. atomoxetine, guanfacine, and clonidine)	X	X	Psychostimulant agents (e.g. methylphenidate and amphetamine), are allowed.
Anaesthetics	General	X	X
	Local	X	General anaesthetics are disallowed during the study except in case of emergency procedures requiring anaesthesia
Analgesics	Narcotic analgesics	X	X
	NSAIDs ^a	X	
Anorexics	X	X	
Anti acne agents	X	X	Agents for topical use are allowed
Antibiotics			Only rifampicin is disallowed
Anticoagulants	X	X	Only low-molecular weight heparins are allowed for episodic use
Anticonvulsants	X	X	
Antidepressants	X	X	Monoamine oxidase inhibitors (MAOs) are contraindicated.
Antidiarrhoeal agents	X	X	Only loperamide, bismuth and kaolin preparations are allowed
Antihistamines	X	X	Only loratadine, desloratadine, cetirizine, levocetirizine, mizolastine and fexofenadine are allowed
Antimigraine agents – triptans, dopamine antagonists	X	X	
Antinauseants (including dopamine antagonists)	X	X	Only phosphoric acid preparations, bismuth and cola syrup are allowed
Antineoplastics	X	X	
Antiobesity agents	X	X	
Antiplatelet treatment (including low dose aspirin)	X	X	
Antipsychotics	X	X	
Anxiolytics	X	X	

Drug Class	Disallowed (X) During the Study for		
	Chronic Use	Episodic Use	Comments or Exceptions
Cough/cold agents	X		Preparations containing ephedrine, pseudoephedrine and codeine are allowed for episodic treatment for a maximum of 1 week
Herbal remedies, which are psychoactive (e.g. St. John's Wort, kava kava, valerian, ginkgo biloba)	X	X	
Hormones	X	X	Only thyroid hormone replacement, contraceptives and progesterone replacement therapy are allowed.
Hypoglycaemic agents		X	
Insulin		X	
Mood stabilisers (including lithium, valproate, valpromide)	X	X	
Muscle relaxant	X	X	
Psychotropic agents not otherwise specified (including, tryptophan, and dopamine agonists)	X	X	
Sedatives/hypnotics ^b	X	X	Zolpidem, zopiclone or zaleplon allowed, for severe insomnia, with a maximum of 2 nights per week. Melatonin is allowed with a maximum of 3 nights per week. The patient is not allowed to take any sleeping aid the night before a study visit.
Systemic steroids	X	X	

- a. Both start and stop dates for each use are to be reported in the eCRF
- b. Both start and stop dates for each use are to be reported in the eCRF. Every tablet/capsule should be reported for this type of medication from the Baseline Extension A Visit until Visit 13.

## List of Abbreviations and Definitions of Terms

ANCOVA	analysis of covariance
APTS	all-patients-treated set
CI	confidence interval
DMC	Data Monitoring Committee
DSM	Diagnostic and Statistical Manual of Mental Disorders
eCRF	electronic case report form
FAS	full-analysis set
IMP	investigational medicinal product
LOCF	last observation carried forward
MDD	Major Depressive Disorder
MedDRA	Medical Dictionary for Regulatory Activities
MMRM	mixed model for repeated measurements
OC	observed case(s)
OLEXA	baseline extension A
PCS	potentially clinically significant
PYE	patient years of exposure
SAE	serious adverse event
SAS®	statistical software package from the SAS® Institute
SOC	system organ class
TEAE	treatment-emergent adverse event

# 1 Objectives

## 1.1 Primary Objective

- Primary objective:
  - to evaluate the long-term safety and tolerability of vortioxetine in child and adolescent patients with a DSM-5TM/diagnosis of MDD

## 1.2 Secondary Objectives

- Secondary objectives:
  - to evaluate the long-term effectiveness of flexible doses of vortioxetine in a range of 5 mg/day to 20 mg/day on:
    - depressive symptoms
    - clinical global impression
    - cognitive function
    - functionality
  - to evaluate the palatability and acceptability of vortioxetine oral drops

# 2 Study Design

This is an interventional, multi-national, multi-site, open-label, flexible-dose, long-term extension study in child and adolescent patients with MDD who completed one of the double-blind, placebo-controlled, active-reference studies 12709A and 12710A.

The Baseline Visit, hereafter referred to as OLEXA, of this extension study, will be Visit 12 (Completion Visit) of lead-in Study 12709A or 12710A, see section 18.1.

The dosage of vortioxetine will be initiated at 5 mg/day for the first 2 days prior to receiving 10 mg/day. The target dose is 10 mg/day; however, the investigator has the possibility to adjust the dose in case of unsatisfactory response up to 20 mg or in case of dose-limiting adverse events. The dose can be up or down titrated with 5 mg/day. The patient should receive the same dose for 2 days before being up-titrated to a new dose. Changes in dosing may occur at any site visit during the treatment course at the investigator's discretion but the maximum dose may not exceed 20 mg/day.

[figure not shown]
For subset of patients participating in the palatability assessment (patients enrolled in Bulgaria, Estonia, Germany, Latvia, Mexico, Poland, Russia, Serbia, Ukraine, and Colombia), palatability and acceptability of vortioxetine oral drops will be assessed after intake of a single dose (5-20 mg) corresponding to the patient's current vortioxetine dose (instead of their vortioxetine tablet on that day). The assessment can be done at any visit to the clinic from Week 4 to Week 18 (i.e., at Visits 5, 7, 9, or 11).

The treatment period is 26 weeks. The total study duration per patient from OLEXA to the end of follow-up will be approximately 30 weeks.

If possible, patients who withdraw are to be seen for a withdrawal visit as soon as possible and they will be contacted for a safety follow-up visit 4 weeks after withdrawal.

The study design is presented in [Panel 1](#).

## Panel 1 Study Design

\*A gray visit number indicates a phone contact

## 3 Endpoints

### 3.1 Primary Endpoint

Safety and tolerability:

- adverse events (AEs)
- PAERS assessment
- Tanner score
- absolute values and changes from OLEXA in clinical safety laboratory tests, vital signs, height, weight and ECG parameters
- length of menstrual cycle

- potentially clinically significant clinical safety laboratory test values, vital signs, weight, and ECG parameter values relative to OLEXA
- C-SSRS categorisation

### **3.2 Secondary Endpoints**

Depressive symptoms:

- change from OLEXA to Week 26 in CDRS-R total score

Global Clinical Impression:

- change from OLEXA to Week 26 in CGI-S score
- CGI-I score at Week 26. The assessment of the CGI-I should be in reference to Baseline A in the lead-in studies. The Baseline A lies 12 weeks prior to OLEXA.

Cognitive function:

Children (7-11 years)

- change from OLEXA to Week 26 in BRIEF using the Global Executive Composite score
- change from OLEXA to Week 26 in BRIEF using the Metacognition Index

Adolescents (12-18 years)

- change from OLEXA to Week 26 in BRIEF-SR using the Global Executive Composite score
- change from OLEXA to Week 26 in BRIEF-SR using the Metacognition Index

Functionality:

- change from OLEXA to Week 26 in CGAS score
- change from OLEXA to Week 26 in PedsQL VAS

Palatability and acceptability:

- absolute value of palatability and acceptability item scores

## **4 Analysis Sets**

The following analysis sets will be used to analyse and present the data:

- all-patients-treated set (APTS) – all patients who took at least one dose of vortioxetine in 12712A.
- full-analysis set (FAS) – all patients in the APTS with valid OLEXA assessment and at least one valid post-OLEXA assessment of the CDRS-R total score.

The safety analyses will be based on the APTS. The efficacy analyses will be based on the FAS.

The patients and data will be classified into the analysis sets according to the definitions above after the study database has been released.

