8.4 Withdrawal Visit

Patients who withdraw from the study prior to the Completion Visit will be asked to attend a Withdrawal Visit, if at all possible. The visit must be scheduled as soon as possible after withdrawal.

No new information will be collected from patients who withdraw, except information collected in relation to the scheduled Withdrawal Visit or needed for the follow-up of adverse events (section 10.5).

The reason for withdrawal must be recorded on the *Reason for Withdrawal Form*.

For a patient and/or his or her legal representative (if applicable) who withdraw assent/consent:

- if the patient and/or his or her legal representative (if applicable) withdraw assent/consent during a visit and then agrees to it being the final visit, the investigator will complete the visit as a Withdrawal Visit and all the data collected up to and including this visit will be used
- if the patient and/or his or her legal representative (if applicable) withdraw assent/consent during a telephone conversation, the investigator will ask the patient if he or she will attend a Withdrawal Visit. If the patient:
 - agrees to attend a Withdrawal Visit, all the data collected up to and including this visit will be used
 - refuses to attend a Withdrawal Visit, the investigator should attempt to follow the patient's safety and future treatment; any information collected will only be recorded in the patient's medical record

- if the patient and/or his or her legal representative (if applicable) explicitly request that his or her data collected from the time of withdrawal of assent/consent onwards not be used, this will be respected

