## 10.2 General Efficacy Analysis Methodology

Unless otherwise specified, all the efficacy analyses will be based on the FAS.

All the tables and graphs will be presented for all patients and by lead-in studies and by lead-in treatments, respectively.

Analysis of the endpoints subjected to inferential statistical methods will be presented with 95% CIs.

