## **18.4 Identifying rows for analysis**

Assessments at Withdrawal Visits will be assigned to a target day according to [Data Handling Plan](#). Unscheduled scale assessments will be windowed in the corresponding way as withdrawal assessments but after any assessments from Withdrawal Visits has been windowed.

Before protocol amendment (PA2), CDRS-R was only assessed at week 0, 12 and 26, however, the same visit window will be applied.

Analysis day will then be mapped based on target day. Analysis week will be analysis day/7.

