## **18.5 Handling Missing or Incomplete Dates/Times**

### **18.5.1 IMP Start and Stop Dates**

In evaluation of valid efficacy and safety assessments (assessment is considered valid if assessment date-date of last IMP  $\leq 7$  days), a missing date of last IMP will be imputed by the latest attended Visit in the study before the safety follow-up.

Exposure with missing IMP start or stop date will not be calculated.

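### Before amendment PA2, patients who left before Week 12 without a valid withdrawal or unscheduled CDRS-R are excluded from every efficacy scale, because one CDRS-R-based FAS serves them all

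*SAP*

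**What the plan says.** SAP section 4 admits to the FAS "all patients in the APTS with valid OLEXA assessment and at least one valid post-OLEXA assessment of the CDRS-R total score". Section 10.2 sets the scope: "Unless otherwise specified, all the efficacy analyses will be based on the FAS". No scale-specific set is defined for CGI-S, CGI-I, BRIEF, CGAS or PedsQL VAS.

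The CDRS-R schedule changed during the study. SAP section 18.4 states: "Before protocol amendment (PA2), CDRS-R was only assessed at week 0, 12 and 26". In the current flow chart (SAP Appendix II) the first post-OLEXA CDRS-R is at Week 1.

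A patient who leaves early has other ways into the FAS:

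- SAP section 18.4 keeps withdrawal data: "Assessments at Withdrawal Visits will be assigned to a target day according to" the Data Handling Plan. Unscheduled scale assessments are then windowed in the same way.
- Protocol section 8.4 says that patients who withdraw "will be asked to attend a Withdrawal Visit, if at all possible".
- Protocol section 8.3 makes the CDRS-R compulsory at an unscheduled site visit requested to discuss the dose.

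All of these are subject to SAP section 18.5.1: "assessment is considered valid if assessment date-date of last IMP" is at most 7 days.

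The FAS definition in Protocol section 17.2 asks only for a valid post-baseline CDRS-R. The SAP adds a valid OLEXA assessment. The four changes listed in SAP section 17 do not include this one.

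**The concern.** Whether a patient's CGI-S or CGAS data are analysed depends on a different scale, and that scale had two schedules. After PA2, a patient who reaches Week 1 can already have a qualifying CDRS-R. Before PA2, no CDRS-R was scheduled between OLEXA and Week 12, so a patient who left in that interval needs a valid withdrawal or unscheduled one.

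The patients at risk are early leavers who did not return promptly. In a single-arm study whose efficacy result is change from OLEXA, leaving them out selects towards patients who stayed. It also conflicts with SAP section 10.3.1, which says the CGI-S MMRM uses all available observations up to completion or withdrawal. A CGI-S value at Week 4 is such an observation, but the FAS condition can remove it.

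The reader of the report would not see this. SAP section 6.1 gives analysis-set counts overall and by lead-in study, not by amendment period, and no sensitivity analysis covers the exclusion.

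**Working it through.** **1. The plan's own figure.** The only related number is the planned enrolment of about 850 (SAP section 15). It follows from 1200 randomised, 15-20% lead-in dropout and at most 85% roll-over:

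- 1200 × 0.85 × 0.85 = 867
- 1200 × 0.80 × 0.85 = 816

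850 lies between them and is used below. The documents give no count of patients lost from the FAS.

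**2. Who is lost.** A patient is excluded from all efficacy scales because of the CDRS-R condition if all of these hold:

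- enrolled under the pre-PA2 schedule;
- left before the Week 12 CDRS-R;
- has no withdrawal CDRS-R within 7 days of the last dose;
- has no valid unscheduled CDRS-R.

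**3. How many.** Number lost = 850 × f × w × m, where f is the share enrolled before PA2, w the share of those leaving before Week 12, and m the share of those leavers with no valid post-OLEXA CDRS-R. None of the three is in the documents. Assumed ranges: f 10-50%, w 5-15%, m 0-100%.

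| f | w | m = 0 | m = 25% | m = 50% | m = 100% |
|---|---|---|---|---|---|
| 10% | 5% | 0 | 1 | 2 | 4 |
| 25% | 10% | 0 | 5 | 11 | 21 |
| 50% | 15% | 0 | 16 | 32 | 64 |

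Central case: 850 × 0.25 × 0.10 × 0.50 = 10.6, or 1.25% of 850. Extreme: 850 × 0.50 × 0.15 × 1.00 = 63.75, or 7.5%. These counts are patients who fail the CDRS-R condition. Those who also have usable data on another scale are at most that many.

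**4. What they could have had on other scales.** On the current flow chart, CGI-S falls at Weeks 1, 2, 4 and 8 before Week 12, and BRIEF, CGAS and PedsQL VAS at Weeks 4 and 8. Whether this was so before PA2 is not stated. SAP section 18.4 names only the CDRS-R as having had the sparse schedule, which is suggestive but not proof.

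**5. Which results can move.**

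| Result | Can the exclusion change it? |
|---|---|
| CGI-S MMRM, including Week 26 | Yes: early values inform the later estimates through the model |
| CGI-S ANCOVA with LOCF | Yes: the last value would be carried forward |
| By-visit results before Week 12, other scales | Yes |
| Baseline efficacy table on the FAS (SAP section 7) | Yes |
| Observed Week 26 means of BRIEF, CGAS, PedsQL VAS | No: an early leaver has no Week 26 value |

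MMRM and LOCF are planned for CDRS-R and CGI-S only (SAP section 10.3.1).

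**The case against.** A reader might infer that pre-PA2 patients who left before Week 12 drop out as a class, or that FAS entry in that cohort meant staying 12 weeks. The documents do not support this. The CDRS-R belongs to the Completion/Withdrawal visit in the flow chart, leavers are asked to attend, and withdrawal and unscheduled values are windowed into the analysis. If every early leaver had a valid CDRS-R by one of these routes, nobody is lost.

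Four further arguments carry weight:

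- **The 7-day rule is not special to the CDRS-R.** It covers efficacy assessments in general, so a late Withdrawal Visit voids that visit's other scales too. Only values from earlier visits are at stake.
- **It is not shown that there are data to lose.** If the other scales were also sparse before PA2, the loss is small or nil. Even on the current schedule, a patient who left before Week 4 without a Withdrawal Visit has no post-OLEXA BRIEF, CGAS or PedsQL VAS value.
- **One FAS for all scales is a legitimate choice.** Protocol section 3.2 calls the CDRS-R the primary efficacy endpoint, and a common population has merit. Efficacy is secondary here, and the primary safety analysis uses the APTS.
- **The added OLEXA condition is close to trivial.** Inclusion criterion 7 requires completion of lead-in Visit 12, whose CDRS-R is the OLEXA value.

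These arguments limit the size and reach of the problem. They do not remove it. A Withdrawal Visit is requested without a day limit, so a CDRS-R more than 7 days after the last dose is foreseeable. The SAP exempts PAERS from the 7-day rule and treats all C-SSRS assessments as valid, but makes no such exception for the CDRS-R. The withdrawal listing shows days in study, but nothing planned separates FAS exclusions by amendment period.

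**Conclusion.** The point holds in a limited form. One CDRS-R-based FAS governs all efficacy scales. It can exclude pre-PA2 patients who left before Week 12 without a valid withdrawal or unscheduled CDRS-R, even where they have valid earlier values on CGI-S or another scale. The main consequence is for the CGI-S MMRM and LOCF ANCOVA, then for the early by-visit results and the FAS baseline table.

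The number excluded cannot be determined from the documents. The range of 0 to about 64 of 850, with about 11 in the central case, rests entirely on the assumed f, w and m, and on CDRS-R having been part of the Withdrawal Visit before PA2 as it is now.

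A reader might also try to turn the exclusion into a bias in score points, for example by supposing that the lost patients did 10 points worse. The documents give no basis for that. Such a difference is impossible on the CGI-S, which runs from 1 to 7, and on BRIEF, CGAS and PedsQL VAS the observed Week 26 means cannot move at all. No bias figure should be attached to this point. It is a cheap improvement to secondary analyses, with no bearing on the primary safety analysis.

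**What to change.** 1. Analyse each scale other than the CDRS-R, at minimum CGI-S, in APTS patients with a valid OLEXA value and at least one valid post-OLEXA value of that scale. This can be the main analysis or a sensitivity analysis beside the FAS. The CDRS-R condition stays for CDRS-R analyses.
2. In the disposition table, report the number of APTS patients excluded from the FAS, split by enrolment before and after PA2.
3. State in the SAP when CGI-S, BRIEF, CGAS and PedsQL VAS were assessed before PA2, so that a reader can tell whether data are lost.
4. List the added OLEXA condition in SAP section 17 as a change from Protocol section 17.2.

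The cost is SAP wording, one extra disposition row and, if the sensitivity route is chosen, a repeat run of existing programs. No new data are needed. The downside is that the N will differ slightly between scales.
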